#### Informed Consent Procedures:

For Objective 1a, the secondary data analysis portion of this aim, we are requesting waiver of informed consent and a HIPAA waiver

For Objective 1b, the Veteran or Caregiver Interviews portion of this objective, a CIRB approved information consent sheet appropriate for the respondent will be mailed to the Veterans with the recruitment packet described above, or as described above to the Caregiver. A waiver of written consent will be requested for all interviews because interviews will be conducted over the phone and are considered minimal risk. Verbal informed consent will be obtained in conformation with the policies established by the CIRB Institutional Review Board in accordance with the Department of Health and Human Services Regulations regarding the protection of human subjects (45 CFR 46.116). The verbal consenting procedure is detailed in each of the interview guides.

## Privacy and Confidentiality:

All secondary data records and all data containing PHI will be stored exclusively on the Providence Research APP26 server. Please see the Data Assurances section of the protocol for a description of the security measures in place for all electronic data.

To help mitigate the risks to Veteran interviewees in Objective 1, telephone interviews will be conducted in private settings as individual interviews with the interviewer and an additional member of the project team. At no time will any content of interviews be discussed with or released to clinicians of Veterans, or ADNA program coordinators. Identifiers, including first and last name and the name of their associated VAMC, will not be elicited from interview respondents during interview recordings. After transcription, the transcripts will be read by a project team member to ensure that any identifiable or sensitive data that participants volunteer during the interviews is removed prior to analysis. Interview responses will be aggregated so individual sites and interviewees cannot be identified. No individually identifiable information will be published or disclosed, unless required by law.

To protect participants against risk after interview data have been collected, we will take a variety of measures to ensure confidentiality. In all records, participants will be assigned unique identifiers. The crosswalk linking unique identifiers to participants, the verbal consent log, as well as all interview recordings and transcripts will be stored electronically in a password protected, restricted-use folder on a Providence VA server in a restricted access service directory, in a restricted folder with access limited to project staff. Any hard copies of any of these files will be stored at the VA in a locked file cabinet in the locked office of study personnel. When the data are reported, neither VAMCs nor interviewees will be identified in any way, to preserve anonymity of respondents.

Please see the Data Assurances section of the protocol for a description of the security measures in place for all electronic data.

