## Description of the VD-HCBS Program.

The research project described in the protocol is an evaluation of the VD-HCBS program. Like the participant-directed programs developed for Medicaid programs (i.e. Money follows the Patient, or Cash and Counseling),  VD-HCBS maximizes Veteran-centered care and independence. VD-HCBS provides Veterans with a monthly financial allotment based on an assessment of the extent of their need for assistance with personal care due to injury or the impact of disease. Veterans have the opportunity to spend their allotment on services that best meet their needs, such as personal care workers whom they hire and manage themselves. Personal care workers may be family members who otherwise may not be able to afford to stay out of the workforce to care for the Veteran. Allotted funds may also be spent on supplies, home modifications, and/or adaptive equipment not available through other VA programs.

ADNAs play a key role in identifying Veteran's needs, coordinating Veteran services, financial reporting, and coordinating with VA. An ADNA coordinator works with the Veteran to 1) develop a person-centered plan for the Veteran's care, 2) identify risks to Veterans' health and safety and include in the plan how Veterans and their caregivers can mitigate those risks, 3) monitor spending and service utilization and 4) provide ongoing options counseling and support to Veterans. In addition, the Veteran (or appointed representative) and the ADNA representative work closely with a Financial Management Service (FMS) to manage employment taxes and insurance and process payroll and timesheets. The ADNA bills the VA for their services and oversight of VD-HCBS recipients.

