# **5.0 Study Procedures**

## Objective 1 –

The purpose of Objective 1 is to understand the impact of the VD-HCBS program on similar outcomes for Veterans using a mixed qualitative and quantitative method design. The quantitative methodology (Objective 1a) will be a secondary data analysis of the ADNA assessments. These data will be obtained via a Data Use Agreement (DUA) with the VHA Office of Geriatrics and Extended Care. These assessments contain surveys that are administered at each Veteran's initial in-home visit, and quarterly thereafter as part of the national roll-out and operation of the VD-HCBS program. PHI is included in this data set including name, social security number, and date of birth., address, phone number, email (if available), and caregiver contact information. All secondary survey data will be stored on the restricted access Providence VA research server, in a restricted folder in accordance with VA policy.

For the qualitative aim (Objective 1b), we will be conducting semi-structured telephone interviews with a random sample of Veterans (n=64) newly enrolled to VD HCBS (to include the sites involved in the roll out and all other sites with VD HCBS) to gain further insight into the ways in which the VD-HCBS program has impacted their lives. Veterans will be interviewed at two time points in 12 months after initiation of VD-HCBS, for a total of 128 interviews. If a Veteran is unable to communicate on the telephone, we will instead contact their caregiver and invite them to share their own experiences with the program. These interviews will be recorded for transcription purposes. Participants will be sent an information consent sheet, however consent for the interviews and the recording will be acquired verbally as detailed in the interviews will be coded as described in the data analysis section.

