For Veterans whom we do not receive a refusal postcard or telephone call, we make no more than three attempts to contact them via telephone between the hours of 10am and 7pm, in their representative time zones.

If it is discovered during these attempts that the Veteran is unable to participate due to medical limitations such as being non-verbal, aphasic, or cognitively impaired, the project team will exclude the Veteran from participation and instead will contact the Veteran's Caregiver as listed in the ADNA survey. At this point, a packet including the introduction letter, refusal postcard, and the CIRB approved Caregiver information consent sheet will be sent to the named caregiver. Receipt of this postcard by the project staff will terminate all future contact with the Caregiver regarding this project.

For Caregivers whom we do not receive a refusal postcard or telephone call, we make no more than three attempts to contact them via telephone at the number listed in the ADNA survey between the hours of 10am and 7pm, in their representative time zones.

If the caregiver agrees to participate in this project, the caregiver will be asked questions regarding their own experiences with the program as described in the Caregivers interview guide and this data will be analyzed separately.

In order to ensure that the appropriate number of Veterans and Caregivers are enrolled, for every instance where we receive a refusal or are unable to make contact with the Veteran or Caregiver, a new Veteran will be randomly selected and the recruitment process will repeat.

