## Reporting:

Any Unanticipated Problems Involving Risks to Subjects or Others, Serious Adverse Events, Protocol Deviations, Apparent Serious Noncompliance, and Information Security Incidents will be reported as outlined in VHA Handbook 1058.01. All staff will be instructed to notify [name] immediately if a problem arises. The ISO and Privacy Officer will be notified within one hour of improper use or disclosure of data.

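### The Objective 1 confidentiality rule has no safety exception, so warning a clinician or ADNA coordinator of a serious danger would depart from the protocol unless the law required the report

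*Combined protocol and SAP*

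**What the plan says.** The privacy text for Objective 1 (section 5.0) sets out how interviews with Veterans, or with Caregivers in their place, are protected. On who may hear what was said, it states: "At no time will any content of interviews be discussed with or released to clinicians of Veterans, or ADNA program coordinators". Four sentences later the same paragraph adds: "No individually identifiable information will be published or disclosed, unless required by law".

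The Reporting text in section 8.0 says that unanticipated problems, serious adverse events, protocol deviations and similar events "will be reported as outlined in VHA Handbook 1058.01". It also has staff notify a named study role at once when a problem arises.

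Section 2.0 describes what the ADNA coordinator does with the Veteran. The tasks include to "identify risks to Veterans' health and safety and include in the plan how Veterans and their caregivers can mitigate those risks" and to "provide ongoing options counseling and support to Veterans".

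**The concern.** The rule shuts out the two parties best placed to act on a danger to the Veteran: the treating clinician, and the coordinator who helps the Veteran plan for safety risks. The Significance text calls these Veterans vulnerable and says that most have functional or cognitive deficits. Section 2.0 adds that they hire and manage their own care workers, who may be relatives. It is foreseeable that an interview about how the program meets a Veteran's needs will bring out a danger at home.

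Staff who hear of one would have to choose between the wording of the protocol and a direct warning. What is at stake is participant safety and the position in which the protocol puts its own staff. No estimate or study conclusion depends on it.

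**Working it through.** No calculation bears on the substance; the check is a reading of the texts against each other. Take one case: a respondent discloses a serious danger, and no law requires a report.

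1. **The rule itself.** Its wording is unconditional about both time and content, and it names clinicians and ADNA coordinators as barred recipients. It carries no exception.

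2. **The legal exception.** This belongs to the sentence on identifiable information, "No individually identifiable information will be published or disclosed, unless required by law", and not to the rule in step 1. It also covers legal duty only. A useful warning has to identify the Veteran, so in the assumed case this second sentence blocks the warning as well.

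3. **The Reporting section.** It opens an internal route and a route under the VHA Handbook. It does not list clinicians or coordinators as recipients, and it does not say that it prevails over the privacy text. Protocol deviations are among its reportable events, so a direct warning would itself be reportable as one.

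4. **Other risk text.** Overview of Risks in section 8.0 names breach of confidentiality as the primary risk. No supplied section sets out what to do about abuse, neglect, self-harm or other danger disclosed by a respondent.

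5. **Routes left open.** The rule binds study staff only. The respondent may tell the clinician or coordinator directly, staff may urge this, and the ADNA remains in contact with the Veteran.

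6. **Where the direct route is weakest.** Recruitment Methods replaces the Veteran with the Caregiver when the Veteran is "unable to participate due to medical limitations such as being non-verbal, aphasic, or cognitively impaired". In those interviews the direct route depends on the Caregiver.

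**Scope.** Section 5.0 gives 64 respondents, each interviewed twice: 64 × 2 = 128, which agrees with the plan's own figure, "for a total of 128 interviews". This counts the interviews under the rule, not the events expected. The documents give no disclosure rate from which to estimate those.

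**The case against.** The strongest reply is that the answer may lie in documents that were not supplied. Of verbal consent the protocol says: "The verbal consenting procedure is detailed in each of the interview guides". A procedure for distress or danger could sit in those guides, in the consent sheets, in the Handbook, or in pages removed before review. That stands as a limit: it cannot be said that the study has no procedure. It does not remove the point, because a procedure that allowed contact with a clinician or coordinator would contradict the protocol sentence, and the two would need to be reconciled.

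A second reply is that both sentences were written to protect people commenting on their own care, and that the second reads mainly as a rule on reporting results. That is a fair account of their purpose. Respondents are discussing a program that ADNA coordinators help run, which is a good reason to keep the rule. The wording still reaches the safety case.

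A third is that the paragraph opens by speaking of Veteran interviewees, so its application to Caregiver interviews is an inference. This is true, but the rule refers to any interview content and sits in the Objective 1 section, so the inference is reasonable.

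A fourth is that the trigger is narrow: a serious danger, raised in a minimal-risk interview, not legally reportable, not resolved by internal escalation, and not raised by the respondent directly. This stands, and it keeps the point minor. A process for reporting deviations after the event does not give permission to act.

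**Conclusion.** The concern holds. As the protocol is written, study staff who told a clinician or ADNA coordinator of a serious danger heard in an Objective 1 interview, where the law did not require the report, would depart from it. The rule applies to 128 interviews if Caregiver interviews are included, as the wording suggests. How often the situation would arise is unknown, and no delay or number of events is claimed.

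The point is minor, and it is held with moderate confidence because the interview guides, consent sheets and Handbook were not available. It concerns a stated rule that gives a worse safety result when followed literally. It has no bearing on the analysis.

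**What to change.** Keep the rule and make three short changes.

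1. **Privacy and Confidentiality, Objective 1.** Add to the rule an exception for disclosures required by law or needed to address a serious risk to the safety of the Veteran or another person, handled under the Reporting section. Extend the legal exception in the sentence on identifiable information to cover this safety exception too; otherwise that sentence would still block a warning that names the Veteran.

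2. **Reporting, section 8.0.** State that the notified study role decides who outside the study is told, including the clinician or ADNA coordinator where appropriate. This leaves room not to tell a coordinator who is the subject of the concern.

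3. **Consent sheets and interview guides.** Align them so that each respondent hears of this limit on confidentiality before the interview begins.

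The cost is a CIRB amendment for the wording and the revision of the consent sheets and guides. Some respondents may be slightly less candid once told of the exception, so it should be kept narrow.

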## **Objective 2**

The second objective of this evaluation is to understand the effect of the VD-HCBS program on Caregivers' well-being. This will be done using telephone surveys with caregivers. Each Caregiver will participate in two 20-minute phone surveys held 12 months apart. These calls will not be audio recorded, but caregiver responses will be entered into the project database using a unique coded ID. A crosswalk to the database will be maintained separately in a restricted access folder on the Providence VA server. We will examine the outcomes for Caregivers of Veterans enrolled in the VD-HCBS program and compare this to a control group of Caregivers using data previously collected as part of the VA CARES evaluation.

Data for the outcomes for Caregivers of Veterans enrolled in the VD-HCBS program will be collected via telephone survey and data from the control group will be acquired following an approved Data Use Agreement with the VA Office of Geriatrics and Extended Care. We will test our working hypothesis through analysis of the telephone surveys and compare them to Caregivers who participated in a previous partnered evaluation of the Caregiver Support Program. With the documented relationship between Caregiver burden, stress, strain and quality of life and the ability for the care-recipient to remain in the home, it is imperative to understand the impact on caregivers as part of the causal chain of program impact for Veterans. When the proposed studies from this objective are completed, it is our expectation that the impact of the VD-HCBS program on Veterans' Caregivers will be better understood. Our proposal for analysis of the Caregiver Survey Data is describe in Section 6.0 (objective 2).

## Recruitment Methods:

This objective will be completed in two separate stages. The first stage will be data collection of caregiver Survey data via telephone surveys. Caregivers of Veterans receiving VD-HCBS will be given a sealed packet during the ADNA's initial visit or will be placed within the Veteran interview packet to be mailed as described above. The sealed packet will be labeled "To the Veteran Caregiver" and will include information about the project, the phone survey, the goal of the project, and provide contact information of a Providence-based project staff member to address any questions or concerns they may have prior to participating. Also included in these letters will be a copy of the informed consent sheet for caregivers to keep and will contain contact information should they have any questions either before or after the survey. In addition, within this introductory packet will be an opt-in postcard that caregivers will be asked to complete and return if they wish to participate or be contacted again regarding this study. A draft of this opt-in postcard is included in the application (Opt-in Postcard included in submission). . Data for the outcomes for caregivers of Veterans enrolled in the VD-HCBS program will be obtained from the VHA Office of Geriatrics and Extended care following an approved Data Use Agreement in accordance with VA Policy. We estimate that there will be approximately 4500 Caregivers' data included in this data set. Data for the control group will be obtained from the VHA Caregiver Support Program following an approved Data Use Agreement in accordance with VA Policy. We estimate that there will be approximately 158 Caregivers (92 approved for the Caregiver Support Program and 66 not approved) with pre and post survey data included in this data set.

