## Recruitment Methods:

All quantitative data will be obtained from the data owners (VHA Office of GEC), following an approved Data Use Agreement in accordance with VHA policy. As

part of standard operations, the ADNA meets with the Veteran initially and every 90 days thereafter. During these meetings it is customary for the ADNA to ask about current services, as well as, unmet needs and satisfaction with the program.

The VD-HCBS program currently enrolls ~825 new Veterans annually at existing sites. At newly opened sites, there is a period between readiness review and enrolling Veterans that delays early recruitment. As a result, we anticipate that ~825 Veterans among the new sites will be enrolled annually. With 4 routine ADNA assessments per Veteran, we expect to receive up to 6,600 surveys.

A total of 64 respondents consisting of Veterans or Caregivers will be recruited for qualitative portion of this objective. Recruitment packets will initially be sent using via US Mail to the Veterans' listed residences in the ADNA assessment data or should the addresses not be listed, by using the listed SSN in the ADNA assessment data to access the national Electronic Health Record (EHR) by way of CAPRI/VistAWeb and/or JLV. We will randomly select four Veterans enrolled in VD-HCBS from each of the 16 VAMCs chosen for the implementation analysis described in Objective 3. Veteran selection will be done by inputting all case numbers at a VAMC into a random number generator. This packet will include an introduction letter, refusal postcard, and the CIRB approved information consent sheet. The letter will inform potential participants about the interview, the goal of the interviews, that the interviews will be recorded for transcription purposes and will provide contact information for a Providence-based project staff member to address any questions or concerns they may have prior to participating. They may also use this telephone number to indicate their refusal to participate.

The CIRB approved information consent sheet for Veterans to keep, will describe the procedures and risks and contain contact information should they have any questions.

Also included will be the refusal to participate postcard. Veterans will be asked to complete and return this postcard if they do not wish to participate in the study. Receipt of this postcard by the project staff will terminate all future contact with the Veteran regarding this project.

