## **Objective 2:**

Quantitative Analysis of Caregiver Survey Data - The primary comparison of interest will be the change in outcomes from the baseline survey to the follow survey between VD-HCBS Caregivers and VA CARES participants. Before testing for change over time, we will examine the frequency distributions for all study variables and appropriate transformations will be carried out whenever violations of normality are determined. Descriptive statistics and bivariate correlations will be computed. Each variable will be tested for leptokurtosis to ensure that there is a sufficient range of scores. Variables found to be significantly leptokurtic will be converted into dichotomous outcomes.

An important issue for longitudinal follow-up analyses is the problem of missing data. Data may be missing for one of two reasons: 1) the Veteran of a Caregiver who participated in baseline is no longer receiving VD-HCBS at the 6-month follow-up period; 2) a Caregiver participant is lost to follow-up because of non-participation. In order to avoid biasing the result by including only Caregivers who complete both surveys, we will first examine whether there are indications that the data are missing completely at random. Specifically, we will compare baseline scores for Caregivers that complete both surveys to those that did not complete the follow-up survey. If no significant differences are observed between completers and those that "dropped out" on the baseline variables, then we will proceed with data analysis of the Caregivers who completed both rounds of the survey. However, if we determine that the data are missing at random, then we will impute the missing data using a multiple imputation technique. If necessary, we will perform sensitivity analysis to examine the plausibility of the missing at random assumption using a pattern mixture approach.

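### Caregivers reached through the mailed Veteran interview packet are first surveyed after enrollment, yet that survey serves as their pre-program baseline in Objective 2

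*Combined protocol and SAP*

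**What the plan says.** Section 5.0, Objective 2, Recruitment Methods gives two routes into the caregiver telephone survey. In one, "Caregivers of Veterans receiving VD-HCBS will be given a sealed packet during the ADNA's initial visit". In the other, the same packet "will be placed within the Veteran interview packet to be mailed as described above". On either route the caregiver must return an opt-in postcard before being called.

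The mailed packet is described in section 5.0, Objective 1, Recruitment Methods: "We will randomly select four Veterans enrolled in VD-HCBS from each of the 16 VAMCs chosen for the implementation analysis". Selection is by "inputting all case numbers at a VAMC into a random number generator", and the packet is posted to "the Veterans' listed residences in the ADNA assessment data", with the health record as a fallback source of addresses. Section 5.0, Objective 1 says those assessments are "administered at each Veteran's initial in-home visit, and quarterly thereafter", and it places the linked Veteran interviews in the 12 months after the program begins.

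Section 7.0, Objective 2 defines the primary comparison as "the change in outcomes from the baseline survey to the follow survey between VD-HCBS Caregivers and VA CARES participants". It treats VD-HCBS caregivers as one group, matches them to controls on variables from the baseline survey, and adjusts the outcome models for baseline values of each measure.

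**The concern.** A baseline for a program effect has to be measured before the program can act. For the mailed route, the plan's own procedure places the first survey after enrollment and the initial visit, possibly by months. The value recorded then may already reflect the program, and the plan uses it in three places: the change score, the propensity score and the regression covariates.

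If caregivers improve soon after start, part of the benefit is absorbed into the baseline. The measured change is then too small, and matching or adjusting on that value removes part of the effect. If taking on the program temporarily raises strain, a survey taken during that period sets an artificially poor baseline and the later change looks too good. In both cases the estimate mixes caregivers observed over different stretches of the program.

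**Working it through.** **1. Timing of the first survey.**
- Mailed route: the Veteran is drawn from all case numbers at a VAMC, and the address comes from assessment data that begin at the initial in-home visit. Contact therefore follows that visit.
- Hand-delivered route: the packet arrives at the initial visit, but the call waits for the postcard and no latest date is set.
- Section 5.0, Objective 2 fixes only the spacing of the two surveys, at 12 months. The missing-data text in section 7.0 speaks of a 6-month follow-up. The two must be reconciled, and neither ties the first survey to program start.
- The nearest covariate in section 7.0 is month of enrollment, which does not measure time from start to first survey. There is no route indicator and no sensitivity analysis by route or timing.

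**2. Reproducing the plan's power table.** Inputs from section 7.0, Objective 2, Power: SD 10 and 55 controls on the Positive Aspects of Caregiving Scale, with n VD-HCBS caregivers. Alpha is not stated; two-sided 0.05 is assumed.

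SE = 10 × √(1/55 + 1/n), and power ≈ Φ(δ/SE − 1.96).

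| n | SE | δ/SE at 4 points | Power | Plan's table |
|---|---|---|---|---|
| 500 | 1.421 | 2.816 | 80.4% | 80% |
| 1,000 | 1.385 | 2.888 | 82.3% | 82% |
| 2,000 | 1.367 | 2.927 | 83.3% | 83% |

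All 12 cells of the table reproduce to within 1 percentage point.

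**3. Effect of late baselines.** Let f be the share of VD-HCBS caregivers who came by mail and g the share of the effect already present at their first survey. The measured contrast is 4 × (1 − f × g). Both f and g are assumptions. For illustration, f uses the 64 interview respondents (4 × 16 sites) as if each yielded one completed caregiver survey.

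| n | f | Contrast, g = 0.5 | Power | Contrast, g = 1 | Power |
|---|---|---|---|---|---|
| 500 | 12.8% | 3.74 | 75.0% | 3.49 | 69.0% |
| 1,000 | 6.4% | 3.87 | 79.8% | 3.74 | 77.1% |
| 2,000 | 3.2% | 3.94 | 82.1% | 3.87 | 80.9% |

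With 32 completers at n = 1,000, power is 81.1% (g = 0.5) or 79.8% (g = 1). If a quarter of 1,000 caregivers had late baselines with g = 0.5, the contrast would be 3.50 and power 71.5%.

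**4. Cost of leaving the 64 out.** At n = 936, power is 82.2% against 82.3%. At n = 436 it is 79.8% against 80.4%. The loss is small because 1/55 dominates the standard error.

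Like the plan's own calculation, these figures ignore matching and covariate adjustment. The further loss from matching on a post-start value is not quantified.

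**The case against.** The strongest reply is that both direction and size are unknown. A reader might infer that the estimate must shrink toward zero and that power falls well below 80%. The documents do not support that. They do not say when caregiver benefit appears. If it accrues steadily, a later 12-month window loses little; if start-up raises strain, change is overstated.

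The size is also uncertain. The figure of 64 is the interview sample, which may itself include caregivers, and is not a count of survey completers. Opt-in would lower it, while replacement of refusals and non-contacts would raise the number of packets mailed. Section 5.0, Objective 1 describes the interviewed Veterans as newly enrolled, which makes it less plausible that the whole effect is already present, although the selection step sets no recency limit. The Gantt chart appears to start Veteran interviews about four quarters before caregiver interviews, so some packets may predate the survey.

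The plan's power statement rests on about 1,000 caregivers, so the 69.0% figure belongs only to the smallest row of its table. Objective 2 also mentions data on about 4,500 caregivers, to be obtained from GEC. At that number the same worst case is 82.8% against 83.9%. How those data relate to the telephone survey is not explained, so the mailed share cannot be determined.

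All of this stands, and it limits the claim about magnitude. It does not turn a survey taken after enrollment into a pre-program baseline.

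A second tempting reading is that every late baseline, including those from hand-delivered packets, should leave the primary analysis at negligible cost. That does not follow either, because the documents do not say how many there would be. Starting from 500, keeping 250 gives 76.6% power and keeping 100 gives 66.4%.

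**Conclusion.** The design point holds. As written, the plan puts post-enrollment values into the baseline for mailed-route caregivers and uses them for change, matching and adjustment, with nothing in place to detect or limit the consequence. Dilution is likely if benefit comes early, but that is a condition and not a finding.

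Under the illustrative 64 completers and two-sided alpha 0.05, the power loss at the plan's n of about 1,000 is 2.5 points (half the effect early) to 5.2 points (all early). It is 5.4 to 11.4 points at 500 and at most about 2.4 points at 2,000. This is a modest bias that is inexpensive to prevent. It is worth correcting because route and timing may not be recoverable if they are not recorded prospectively.

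**What to change.** - Record each caregiver's recruitment route, the date VD-HCBS services start and the date of the first survey.
- Define in section 7.0 a fixed baseline window relative to the service start date.
- Exclude mailed-route caregivers whose first survey falls outside the window from the primary Objective 2 analysis, and include them in a sensitivity analysis.
- For hand-delivered packets, schedule the first call within the window. Keep these caregivers in the primary analysis, describe days since start, and report a sensitivity analysis limited to in-window baselines.

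The cost is a few data fields and some analysis-set wording, plus under 1 percentage point of power if as many as 64 mailed-route caregivers are dropped. The cost of also excluding late hand-delivered caregivers cannot be bounded from the documents, which is why that restriction is left to the sensitivity analysis.
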